J.1.1. Primary Primary Outcome (30 Day Mortality): All randomized subjects will be included in the analysis to test the differences in 30 day mortality. 30 day mortality will be computed at the end of study and stated as a dichotomous variable. For subjects who have not been reported as deceased by day 30 following admission from any of the sources queried we will use multiple imputation under the assumption that the missing data are not missing at random. The process for determining whether or not a subject is deceased at 30 days is described in detail in section (N.6.). If more than 15% of the subjects are missing the 30 day outcome, we will consider this outcome as descriptive only. We will analyze this endpoint as a fixed point in time using a two-sided Mantel-Haenszel (M-H) test taking site, the stratifying variable (strata), into account. The M-H test is robust to lack of homogeneity of odds ratio although power would be reduced. This approach has more power than the survival analysis described below given the potential for crossing hazard functions. We will also test homogeneity of the odds ratios across sites using the Breslow-Day test. We will compute 95% confidence intervals on mortality by treatment group at 30 days. We will also conduct a sensitivity analysis of 30 day mortality to assess the effect of imputation 'as alive' on the treatment group comparisons and confidence limits for the 30 day outcome. To provide further insight we will compute 30-day survival curves. Survival time will be compared between treatment arms using Cox proportional hazards model with site as a covariate. If the proportional hazards assumption is violated we will include a time treatment interaction in the model and choose the appropriate approach. As an additional analysis, we will use the same Cox proportional hazards approach to adjust for baseline covariates such as demographics, injury severity, presenting vital signs, and prehospital time. Since site is a stratifying variable it will be included as a random effect. We will do pre-screening of covariates other than site at the 0.20 level before fitting the final model if our sample size is not sufficient to include all covariates in the model. We would follow the approach above to test for and take crossing hazards into account if applicable. As an additional exploratory analysis we will compare 30-day survival in the two groups adjusting for the covariates listed above and any additional baseline covariates that are imbalanced between treatment groups ($p < 0.10$) using the same screening approach to decrease the number of covariates included in the model, if necessary.

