
J.2. Analysis of Prehospital Randomized Secondary Outcomes: Unless there is sufficient power (predetermined before the analysis is begun), the approach to analysis of secondary endpoints will generally be calculation of confidence limits on intervention group differences or model parameters rather than formal tests of significance at a specified critical level as the trial will not have sufficient power to detect difference in all of these outcomes. However, these comparisons will add to the knowledge of the benefits and risks of the interventions. Parametric and nonparametric comparisons will be applied according to normalcy. All tests used will be two-tailed tests at significance level (α) of 0.05. For prehospital randomized clinical outcomes we will use Chi-square with 95% confidence intervals for dichotomous outcomes and parametric or non-parametric testing for continuous variable with 95% confidence intervals. For prehospital randomized laboratory or exploratory outcomes we will use parametric or non-parametric testing for continuous variable with 95% confidence intervals.

J.3. Analysis for Second Stage In-hospital Randomized Dosage Regimens: Chi-square test will be able to test the effect of different tranexamic dosage regimens on hyperfibrinolysis. Similarly, chi-square will be used to detect any differences between dosage groups for 30 day mortality. To detect a trend in dosage response, test for trend will be implemented. As additional analysis and to account for site and to adjust for some important covariates, we will use logistic regression to test the effect of dosage on hyperfibrinolysis. Similarly Cox proportional hazards regression can be used for 30 day mortality. *For In-hospital randomized dosage regimen comparison for clinical outcomes* we will use Chi-square with 95% confidence intervals for dichotomous outcomes and parametric or non-parametric testing for continuous variable with 95% confidence intervals. *For In-hospital randomized dosage regimen comparison for laboratory or exploratory outcomes* we will use parametric or non-parametric testing for continuous variable with 95% confidence intervals.

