J.7. Missing Data: For 30-day mortality, given the transient nature of many of the subjects, extensive efforts will be made to ascertain vital status (see N.6.). Batch searches of the mortality databases will continue every quarter for subjects with unknown status, until trial closeout. For interim and final analyses, subjects who have not been reported as deceased by day 30 following ED admission from any of these sources we will use multiple imputation for the final value. As sensitivity analyses we will report the data with and without imputation. We will also report an analysis consistent with that used in other studies counting those missing as alive on day 30.

K. Sample Size Justification and Power Analysis:

We have determined the sample size for this proposal and powered the analysis based upon the primary outcome, 30 day mortality.

K.1. Primary Outcome 30 day mortality: Assuming a baseline mortality risk of 16% as was demonstrated in the Crash-2 study^{41,43} with 30 day mortality as the primary outcome, using a two-sided Z test with pooled variance and a 2 sided alpha of 0.05 the study will have a 90% power to detect a 7% or greater difference in 30

day mortality. The study will have 80% power to detect a 6% or greater difference in 30 day mortality. Using this power analysis, **497 patients in each arm, 994 total patients will be required, with a power of 0.85 and 2 sided alpha of 0.05. This will require on average each center to enroll 80 patients per year or 1 to 2 per week.** As busy, level 1 trauma centers with robust emergency medical programs were screened using the proposed inclusion criteria over 2012 data and selected for participation based upon this information, this sample size estimate is appropriate and attainable.

Power	Sample Size Grp 1 N1	Sample Size Grp 2 N2	Prop H1 Grp 1 or Trtmnt P1	Prop Grp 2 or Control P2	Diff if H0 D0	Diff if H1 D1	Target Alpha	Actual Alpha	Beta
0.9000	497	497	0.0919	0.1600	0.0000	-0.0681	0.0500		0.1000
0.8500	497	497	0.0965	0.1600	0.0000	-0.0635	0.0500		0.1500
0.8000	497	497	0.1003	0.1600	0.0000	-0.0597	0.0500		0.2000

L. Human Subjects:

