A summary report of the DSMB's findings will be submitted to regulatory agencies. At least one specialized clinician from the Data Safety Monitoring committee will be responsible for monitoring data safety. All related unanticipated problems will be directly handled by study's PIs and reported accordingly. We will also follow Department Of Defense Unique requirements documentation. The University of Pittsburgh and each participating center will have an AE logbook to record and to assure adequate attention for continuous assessment, analysis, and reporting of adverse effects using a standardized report form. The coordinating center will be responsible for all oversight of these risk assessments with monthly evaluations.

P.4. Interim Analyses: In concert with the DSMB, prior to initiation of the trial, the final monitoring plan will be developed to serve as the guide to the DSMB's decision-making process concerning early stopping of the trial. We will recommend interim analyses as 1/3 and 2/3 of patient enrollment. In making the decision to recommend termination of the study, the DSMB shall be guided by several types of information: (i) a formal stopping rule based on the primary analysis (comparison of treatment groups on the in-hospital mortality and 24 hour blood transfusion requirements), (ii) information on safety outcomes by treatment group, (iii) consistency between results for primary and secondary outcomes, and (iv) consistency of treatment effects across subgroups. Formal interim analyses will be performed at 6 months and then annually throughout enrollment. The DSMB will use the results of implementing the stopping rule as a guideline in evaluating the evidence for treatment effects. In making a recommendation to terminate the study, the DSMB will also consider information on safety outcomes, as well as consistency of outcomes for secondary outcomes and consistency of outcomes within important subgroups as described previously. The group sequential method described by O'Brien and

Fleming will be used to develop stopping rules to limit the impact of repeated testing on the probability of a Type I error.⁹⁵

Based on our power analysis, sample sizes of 497 in interventional group and 497 in control group can achieve 80% power to detect a difference of 0.06 between the group proportions of 0.10 and 0.16 at a significance level (alpha) of 0.05 using a two-sided z-test.

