We have proposed two interim analyses in this trial. We have based our testing on group sequential design that dividing patient entry into a fixed number of equal-sized groups and provides ethical and practical ways to make decision to stop the trial or continue based on repeated significance tests of the accumulated data after each group is evaluated.

According to the above power calculation and following the group sequential method described by O’Brien and Fleming in developing stopping rules to limit the impact of repeated testing on the probability of a Type I error, we will have equally spaced looks at 33%, 67% and 100% of patient accruals. This is equal to 166, 332, and 497 subjects in each group at these three looks. The following table and graph provide in details information in relation to alpha spending functions to determine the test boundaries according to O’Brien-Fleming method.

Details when Spending = O'Brien-Fleming, N1 = 497, N2 =497, P1 = 0.10, P2 = 0.16

Look	Time	Lower Bndry	Upper Bndry	Nominal Alpha	Inc Alpha	Total Alpha	Inc Power	Total Power
1	0.33	-3.71030	3.71030	0.000207	0.000207	0.000207	0.018687	0.018687
2	0.67	-2.51142	2.51142	0.012025	0.011890	0.012097	0.399207	0.417894
3	1.00	-1.99302	1.99302	0.046259	0.037903	0.050000	0.382494	0.800388
Drift 2.82089								

Look: These are the sequence numbers of the interim tests.

Time: These are the time points at which the interim tests are conducted. This is also related to proportion of subject accruals

Lower and Upper Boundary: These are the test boundaries. If the computed value of the test statistic z is between these values, the trial should continue. Otherwise, the trial can be stopped.

[figure not shown]
Nominal Alpha: This is the value of alpha for these boundaries if they were used for a single, standalone test. Hence, this is the significance level that must be found for this look in a standard statistical package that does not adjust for multiple looks.

Inc Alpha: This is the amount of alpha that is *spent* by this interim test. It is close to, but not equal to, the value of alpha that would be achieved if only a single test was conducted. The difference is due to the correction that must be made for multiple tests.

Total Alpha: This is the total amount of alpha that is used up to and including the current test.

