Our trial's lower and upper stopping boundaries have been computed to ensure that the trial Type I and Type II error probabilities of the group sequential plan are according to the study assumptions and design. The upper boundaries are related to the formal efficacy testing at each assigned sample size (expected number of primary events completion at 33%, 67%, and 100%). The lower boundaries are related to the formal futility (safety) testing at each assigned sample size (expected number of primary events completion at 33%, 67%, and 100%). Upper and lower boundaries will be provided to DSMB as a guideline and could be modified by DSMB prior to the trial upon reasonable justifications. With this sequential testing plan based on O'Brien-Fleming spending function, only an absolutely overwhelming treatment intervention can justify the termination of our clinical trial after a third of the subjects have been enrolled and completed a one month of follow up. If the trial has been ordered to stop early because of interim analysis, adjusted p-values will be computed based on the described analysis of our main clinical outcome. Unadjusted p-value will not be considered for final results interpretations.

Our interim analysis is part of our three sequential testing as we have mentioned above. At each of the two interim looks, 30 days-mortality will be pooled across participated centers comparing between the two study groups. Based on the assumed power analysis at each interim look, the z-value will be calculated and checked against the upper and lower values guide lines for that specific check. We have illustrated z-values for the upper and lower boundaries across interim two analyses and final analysis of a total accumulated alpha of 0.05. (Figure and Table below)

Details when Spending = O'Brien-Fleming, N1 = 497, N2 = 497, P1 = 0.10, P2 = 0.16

Look	Time	Lower Bndry	Upper Bndry	Nominal Alpha	Inc Alpha	Total Alpha	Inc Power	Total Power
1	0.33	-3.71030	3.71030	0.000207	0.000207	0.000207	0.018687	0.018687
2	0.67	-2.51142	2.51142	0.012025	0.011890	0.012097	0.399207	0.417894

3 1.00 -1.99302 1.99302 0.046259 0.037903 0.050000 0.382494 0.800388
 Drift 2.82089

Look: These are the sequence numbers of the interim tests.

Time: These are the time points at which the interim tests are conducted. This is also related to proportion of subject accruals

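### The plan names no between-arm estimate or interval for 30-day mortality, and after an early stop it corrects only the p-value

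*Combined protocol and SAP*

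**What the plan says.** Section J.1.1 analyses 30-day mortality as a yes/no outcome with a two-sided Mantel-Haenszel test stratified by site, and adds a Breslow-Day test that the odds ratios agree across sites. For precision it says: "We will compute 95% confidence intervals on mortality by treatment group at 30 days". It names no risk difference, risk ratio or common odds ratio as the primary estimate.

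Two other parts of J.1.1 come near the point. The sensitivity analysis that counts missing patients as alive refers to comparisons between groups and to confidence limits, without saying limits on what. A Cox model with site as a covariate is planned for further insight, with no interval stated.

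For secondary outcomes, J.2 describes the general approach as "calculation of confidence limits on intervention group differences or model parameters rather than formal tests of significance".

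On early stopping, Appendix 4, item 1 says: "If the trial has been ordered to stop early because of interim analysis, adjusted p-values will be computed based on the described analysis". It adds that unadjusted p-values will not be used for interpretation. Neither P.4, the DSMB charter nor the rest of Appendix 4 mentions an adjusted estimate or interval.

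**The concern.** The primary objective (E.2) is the effect of prehospital tranexamic acid compared with placebo. An interval on each arm's mortality does not estimate that effect, and the reader cannot recover a site-stratified contrast from two arm-level intervals. If the effect measure stays open, it can be chosen after the results are known.

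The second gap matters more. A trial that stops at a boundary does so because the observed difference happened to be large, so the unadjusted difference at that moment is too large on average. The plan accepts this for the p-value and leaves the other two reported quantities unaddressed. A mortality trial stopped early for benefit would be quoted for its estimate of deaths prevented at least as much as for its p-value.

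**Working it through.** **Inputs.** K.1 gives the test ("two-sided Z test with pooled variance and a 2 sided alpha of 0.05"), the control rate ("Assuming a baseline mortality risk of 16% as was demonstrated in the Crash-2 study") and the size ("497 patients in each arm, 994 total patients will be required, with a power of 0.85 and 2 sided alpha of 0.05"). P.4 gives the effect behind the sequential design: "detect a difference of 0.06 between the group proportions of 0.10 and 0.16 at a significance level (alpha) of 0.05 using a two-sided z-test". It also gives the timing: "we will have equally spaced looks at 33%, 67% and 100% of patient accruals", that is 166, 332 and 497 per arm. The boundaries in P.4 and Appendix 4 are |z| = 3.71030, 2.51142 and 1.99302, with drift 2.82089. A true 13% v 16% is my assumption, to show the range.

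**1. The plan's own figures reproduce.**
- Fixed-sample power for 10% v 16% with 497 per arm, pooled variance: 0.804 (stated 80%).
- Cumulative alpha, 4[1 − Φ(z₁₋α/₄/√t)] with α = 0.05: 0.000207 at t = 1/3 and 0.012097 at t = 2/3, as stated.
- Nominal alpha, 2[1 − Φ(b)]: 0.000207, 0.012025 and 0.046259, as stated.
- Simulated power at the stated drift: 0.8005 in total (stated 0.800388), made up of 0.0187, 0.3995 and 0.3823.

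The design is sound. The point concerns reporting only.

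**2. Difference needed to stop.** With overall mortality near the planned 13%, the standard error of the difference is √(2 × 0.13 × 0.87 / n):
- Look 1: 3.71030 × 0.0369 = 13.7 points (12.2 if the control arm is held at 16%).
- Look 2: 2.51142 × 0.0261 = 6.6 points (6.5 with control at 16%).
- Final look: 1.99302 × 0.0213 = 4.3 points.

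At these mortality levels, an interim stop for benefit needs an observed difference above the 6-point design effect.

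**3. Unadjusted results by stopping point.** Two million simulated binomial trials per scenario used the pooled z at each look and the stated boundaries. The interval is the difference ± 1.96 standard errors.

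| True rates | Stopping point | Probability | Mean difference (points) | Coverage of 95% interval |
|---|---|---|---|---|
| 10% v 16% (true 6) | Look 2 | 40.4% | 8.33 | 95.4% |
| | Look 1 or 2 | 41.9% | 8.57 | 92.0% |
| | All trials | 100% | 6.40 | 94.1% |
| 13% v 16% (true 3) | Look 2 | 7.7% | 8.03 | 68.6% |
| | Look 1 or 2 | 7.8% | 8.16 | 67.5% |
| | All trials | 100% | 3.14 | 94.4% |

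The excess after an early stop is 8.57 − 6 = 2.6 points in the first case and 8.16 − 3 = 5.2 points in the second. A normal-approximation (Brownian motion) calculation agrees closely: 41.8% stop early with a mean of 8.6 at a true 6, and 8.7% with a mean of 7.8 and 70.5% coverage at a true 3. At look 1 an unadjusted interval almost never covers the truth, but the chance of stopping there is only 1.5% to 1.9% at a true 6.

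**4. What per-arm intervals show at full size.** Take 55 v 78 deaths of 497. The pooled rate is 133/994 = 0.1338, so z = 0.0463/0.0216 = 2.14 and p = 0.032, beyond the final boundary. The arm intervals (Wilson) are 8.6–14.1% and 12.8–19.2%. The difference is 4.6 points, 95% interval 0.4 to 8.9. Only that last line answers the trial's question, and the plan does not call for it.

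**5. Level of the final interval.** Appendix 4 pairs z = 1.993 with a final p-value of 0.038. Its own table gives nominal alpha 0.046259 for that boundary; 0.037903 is the incremental alpha. An interval built on 1.993 is 1.993/1.96 = 1.017 times as wide as one built on 1.96.

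**The case against.** The strongest reply is that this is an omission that any competent analyst would fill. The Breslow-Day test implies an odds ratio, the Cox model would normally be reported with a hazard ratio and interval, and the sensitivity analysis speaks of confidence limits alongside group comparisons. Nothing forbids a between-arm interval. Much of this stands: the fault is that the quantity is not specified. But the Cox model is secondary to the Mantel-Haenszel test in J.1.1, and the limits in the sensitivity analysis are undefined.

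Several stronger readings are tempting, and the documents do not support them:
- **That the plan commits to unadjusted estimates after an early stop.** Appendix 4 is silent on estimates.
- **That secondary outcomes are better served.** J.2 offers limits on differences as a general approach where power is lacking, and its specific line for dichotomous outcomes does not say what the interval is on. The primary outcome has the powered, stratified test.
- **That overlapping arm intervals contradict a significant test.** They do not. Reading overlap as no effect is a known mistake. Near the design effect (50 v 80 deaths, p = 0.005) the intervals of 7.7–13.0% and 13.1–19.6% do not overlap at all.
- **That the mortality effect will be exaggerated in general.** Over all trials the bias is +0.4 points at a true 6 and +0.1 at a true 3. At the design effect, even a look-2 stop leaves unadjusted coverage at about 95%.
- **That 1.96 against 1.993 is a material error.** It matters only for a final z between the two.

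**Conclusion.** The concern holds as a gap in specification. J.1.1 leaves the between-arm effect and its interval undefined, and Appendix 4 corrects one of the three quantities that would be reported after an early stop. Alpha, power and the stopping boundaries are unaffected.

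The size depends on whether the trial stops early. Under the design assumption that happens in about 42% of trials, with an average unadjusted difference about 2.6 points too large. With a true difference of half that size it is uncommon (about 8%), but the estimate is then more than two and a half times the truth (8.16/3 = 2.7) and the interval covers in about two trials of three. If the trial runs to full size, the consequence is mainly an unnamed estimate.

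These figures assume looks at exactly 166, 332 and 497 per arm, no futility stopping, no site effects and no missing outcomes. They use the pooled z without the continuity correction mentioned in Appendix 4; that correction would make early stops slightly rarer and the differences at them slightly larger.

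**What to change.** 1. **J.1.1:** name the site-stratified Mantel-Haenszel risk difference, with the common odds ratio beside it, as the primary estimate, and state its interval. Keep the per-arm intervals as description.
2. **Appendix 4, item 1:** beside the adjusted p-value, specify the median-unbiased estimate and interval by stage-wise ordering, used at whichever look the trial ends. One method at every look means that only one interval governs. Repeated confidence intervals (estimate ± boundary × standard error) should not be added as a second rule: they would widen the interval by 2.51142/1.96, about 28%, at look 2, cover in 97.4% of trials at the design effect, and leave the point estimate uncorrected.
3. **Level:** tie the final-look interval to the 1.993 boundary (nominal 0.0463), so that it excludes zero exactly when the boundary is crossed. Correct the sentence in Appendix 4 that pairs 1.993 with 0.038.

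The cost is a few sentences and some additional analysis with standard software. Sample size, data collection and conduct do not change. At the final look the interval is about 2% wider. After an early stop the interval is wider and the estimate less favourable than the unadjusted one.

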E3.1. Secondary Aim#1: Determine whether prehospital tranexamic acid as compared to placebo reduces the incidence of hyperfibrinolysis (estimated percent lysis > 7.5%), acute traumatic coagulopathy (ATC, presenting INR > 1.4), improves PT measurements and additional r-TEG parameters, D-dimer levels, activated Protein C levels, and plasmin-antiplasmin complexes.

Secondary Hypothesis 1: Prehospital tranexamic acid as compared to placebo will reduce the incidence hyperfibrinolysis (estimated percent lysis > 7.5%), reduce the incidence of patients with an arrival INR > 1.4, improve PT and additional presenting r-TEG parameters of coagulopathy including ACT, r-value, k-time, α -angle, maximal amplitude (MA) and G-values and D-dimer levels, activated Protein C levels and plasmin-antiplasmin complexes.

E.3.2. Secondary Aim#2: Determine whether prehospital tranexamic acid as compared to placebo results in a lower incidence of 24 hour mortality, acute lung injury, multiple organ failure, nosocomial infection, early seizures, pulmonary embolism, shock parameters and early resuscitation and transfusion requirements.

Secondary Hypothesis 2A: Prehospital tranexamic acid as compared to placebo will reduce the incidence of 24 hour and 30 day mortality, acute lung injury, multiple organ failure, nosocomial infection, early (24hr) seizures and in-hospital pulmonary embolism.

Secondary Hypothesis 2B: Prehospital tranexamic acid as compared to placebo will improve presenting base deficit, 24 hour crystalloid requirements and reduce 6 hour and 24 hour blood and blood component transfusion requirements (PRBC, FFP and platelets).

E.3.3. Secondary Aim #3: To investigate potential novel mechanisms by which tranexamic acid alters the inflammatory response to injury independent of effects on hyperfibrinolysis. Investigations of the effects of tranexamic acid on inflammation will include analysis of platelet and leukocyte activation via flow cytometry, measurements of plasmin levels and subsequent plasmin mediated complement activation and the early inflammatory cytokine response to trauma.

Secondary Hypothesis 3A: Prehospital tranexamic acid as compared to placebo will reduce plasmin levels and markers of platelet and leukocyte activation measured by flow cytometry (FACS) and result in a plasmin mediated reduction of complement activation as measured by C3a and Factor B levels.

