I.2 Secondary Clinical Outcomes: Secondary clinical outcomes will include the incidence of hyperfibrinolysis (EPL > 7.5% by rapid-TEG analysis) upon arrival to the trauma bay within the first 6 hours, the incidence of acute traumatic coagulopathy (INR > 1.4), 24 hour mortality, acute lung injury, multiple organ failure, the development of nosocomial infection, early (24hr) seizures, in-hospital pulmonary embolism, presenting base deficit, 24 hour crystalloid requirements and 6 hour and 24 hour blood and blood component transfusion requirements (PRBC, FFP and platelets). *These same clinical outcomes will similarly be used for the randomized tranexamic acid dosage regimen comparison.*

I.3. Secondary Laboratory/Mechanistic Outcomes: All laboratory/mechanistic outcomes will be measured during the first 6 hours from trauma center arrival and at 12 and 24 hours (+/- 12 hours) out from injury. Those laboratory/mechanistic outcomes including flow cytometry which require fresh blood samples will be performed only at the University of Pittsburgh on a subset of patient samples unless participating centers have specific capabilities and following appropriate training for standardization. *These same laboratory/mechanistic outcomes will similarly be used for the randomized tranexamic acid dosage regimen comparison at 12 and 24 hours post-injury.*

I.4. Clinical Outcomes Methods/Definitions: All clinical outcomes will be prospectively evaluated for throughout ICU and hospital admission and the timing from the day of initial injury will be recorded for time-to-event statistical analysis.

I.4.1. 30 day and 24 hour mortality: 30 day mortality will be prospectively recorded from the day of trauma bay arrival. Over the first 24 hours we will document and record the time of death in hours. We suspect that patients enrolled will have a significant percentage of mortality that occurs in the first 24hrs.

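### The supportive adjusted Cox models call 'presenting vital signs' baseline without fixing them before the bolus, and they leave the covariate list open to p-value selection

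*Combined protocol and SAP*

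**What the plan says.** Section J.1.1 makes the primary analysis of 30-day mortality a "two-sided Mantel-Haenszel (M-H) test taking site, the stratifying variable (strata), into account". It then adds a Cox model with site as the only covariate. After that comes a supplementary Cox model to "adjust for baseline covariates such as demographics, injury severity, presenting vital signs, and prehospital time", with site as a random effect. *Presenting* is not defined and no measurement time is given.

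Two selection rules follow. The first is a fallback: "pre-screening of covariates other than site at the 0.20 level before fitting the final model if our sample size is not sufficient" to carry every covariate. No criterion for insufficiency is stated. The second belongs only to a further model: "As an additional exploratory analysis we will compare 30-day survival in the two groups adjusting for the covariates listed above", plus "any additional baseline covariates that are imbalanced between treatment groups" at p < 0.10. Because that model carries the listed covariates forward, it also includes presenting vital signs.

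Elsewhere, section E.3.1 names as an outcome "acute traumatic coagulopathy (ATC, presenting INR > 1.4"), and section I.2 lists among the secondary clinical outcomes "presenting base deficit, 24 hour crystalloid requirements".

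**The concern.** A baseline covariate has to be fixed before treatment starts. Sections H.3.1 and H.5.1 place randomization and the first infusion during transport, so a vital sign taken at the trauma center comes after treatment. If tranexamic acid reduces early shock, arrival blood pressure and heart rate lie on the path from treatment to death. Adjusting for them removes that part of the effect from the hazard ratio. Arrival pressure also reflects later care, since section H.7 makes post-intervention crystalloid depend on systolic pressure.

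The open covariate list is a different problem. If the data decide which covariates enter, the adjusted estimate cannot be fully specified in advance, and another analyst could reach a different model from the same plan.

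At stake are the plan's only covariate-adjusted mortality estimates for the prehospital comparison. Readers often turn to such estimates when the arms look unbalanced.

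**Working it through.** **1. The plan's own figure.** Section K.1 gives 497 per arm, 16% against 9.65%, two-sided alpha 0.05, power 0.85. With pooled variance, z = [0.0635 × √497 − 1.960 × √(2 × 0.12825 × 0.87175)] / √(0.0965 × 0.9035 + 0.16 × 0.84) = (1.4156 − 0.9268) / 0.4707 = 1.038, so power is 0.8505. The figure reproduces. It uses no covariates, so nothing below changes it.

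**2. How the protocol uses *presenting*.**

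| Place | Use |
|---|---|
| Synopsis; I.5.1 | Presenting INR, a result treatment should improve or a coagulation outcome |
| E.3.1, aim and hypothesis | Presenting INR in the aim, arrival INR in the matching hypothesis; presenting r-TEG values |
| E.3.2, hypothesis 2B; I.2 | Presenting base deficit, which treatment should improve |
| J.1.1 | Presenting vital signs, called baseline |
| N.2 | Prehospital vital signs collected; no timing relative to the bolus |
| N.3 | Arrival vital signs collected under an emergency-department label |
| Appendix 4, Table 2 | Lowest prehospital systolic pressure; could fall before or after the bolus |

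Where the word describes any other measurement, it means a trauma-center value after the bolus. No entry gives a vital-sign covariate fixed before the bolus.

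**3. What post-bolus adjustment could do (illustration; the mediation inputs are assumed).** The design hazard ratio is ln(1 − 0.0965) / ln(1 − 0.16) = 0.582, log −0.541. A simulation used a total log effect of −0.535, control mortality near 16%, censoring at day 30, and 40,000 patients per row. The arrival value was M = 0.5B + dT + √0.75·e, where B is the pre-bolus value, T is treatment and e is noise. The log hazard was (−0.535 − d·b)T + b·M.

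| Shift d (SD) | b per SD | Unadjusted HR | Adjusted, pre-bolus | Adjusted, arrival |
|---|---|---|---|---|
| 0 | −0.3 | 0.584 | 0.583 | 0.581 |
| 0 | −0.6 | 0.582 | 0.580 | 0.568 |
| 0.1 | −0.3 | 0.575 | 0.576 | 0.593 |
| 0.1 | −0.6 | 0.593 | 0.590 | 0.627 |
| 0.2 | −0.3 | 0.581 | 0.581 | 0.614 |
| 0.2 | −0.6 | 0.605 | 0.604 | 0.674 |
| 0.3 | −0.3 | 0.584 | 0.582 | 0.634 |
| 0.3 | −0.6 | 0.614 | 0.614 | 0.725 |

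Each row is one simulated data set, so compare within rows. The model itself implies arrival-adjusted values from exp(−0.535 + 0.03) = 0.60 to exp(−0.535 + 0.18) = 0.70 for shifts of 0.1 to 0.3 SD; the wider simulated range is sampling noise. With no shift there is no attenuation. Pre-bolus adjustment stays within 0.004 of unadjusted throughout, given the assumed correlation of 0.5.

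**4. The imbalance rule.** With k independent covariates and no true imbalance, the chance that p < 0.10 flags at least one is 1 − 0.9^k: 0.41 for k = 5, 0.65 for k = 10, 0.88 for k = 20.

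**5. Room for a fixed list.** Expected deaths are 497 × (0.16 + 0.0965) = 127 with the K.1 rates, or 497 × (0.16 + 0.10) = 129 with the P.4 rates. At about 10 events per parameter (a rule of thumb), that is 12 to 13 in all; with one for treatment and a small margin, roughly 10 to 12.

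**The case against.** The best defense is that the arrival reading is an inference. INR, r-TEG and base deficit are laboratory values the trial obtains only after arrival, whereas vital signs exist before arrival and determine eligibility (H.2.1). Sections N.2 and N.3 use other labels, and J.1.1 itself says baseline. This stands: a reader might infer that the plan definitely adjusts for arrival values, and the documents do not settle that. What they do show is that no time anchor is given, so the plan permits it.

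The selection rules are also narrower than they first look. The 0.20 screen is conditional, and with the expected deaths its condition may never be met. The p < 0.10 rule sits only in an analysis labeled exploratory. A reader might infer that p-value selection adjusts away the treatment effect. It does not: selecting among true baseline covariates makes the model data-dependent, while attenuation comes only from post-bolus covariates.

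Finally, no decision rests on these models. The Mantel-Haenszel test and the site-only Cox model are specified separately, and Appendix 4 bases stopping on a z-test of 30-day mortality. This stands in full and sets the severity.

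Prehospital time is the weaker example. It can include transport after the bolus, but the documents give no reason why a blinded infusion would change it.

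**Conclusion.** The point holds as a minor one, confined to the supportive adjusted Cox models. Their vital-sign covariate is called baseline without being fixed before the bolus, and the protocol's own vocabulary makes a post-bolus reading plausible. On that reading the adjusted hazard ratio can move toward 1.

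A reader might take a figure from the illustration as the expected bias. The documents do not support one: they contain nothing on how far tranexamic acid shifts arrival vital signs or how strongly those predict death, and with no shift the attenuation is zero. Nor do they support reading this as a threat to the primary result. The primary test, 994 patients, the stated power and the interim boundaries do not use these covariates.

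The open list and the two p-value rules are a separate weakness: the adjusted estimate is not fixed in advance.

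**What to change.** In J.1.1, define the vital signs as the last systolic pressure and heart rate recorded before Bag A starts. Do not rely on the qualifying values: eligibility needs hypotension or tachycardia, so they may not supply both.

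Replace the open-ended wording with a short list fixed before unblinding, within roughly 10 to 12 parameters, and delete the 0.20 screen and the p < 0.10 imbalance rule.

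Replacing prehospital time with time from injury to bolus is optional. It depends on the bolus time being captured, which section N.2 does not list, and injury time is itself an estimate.

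The main cost is analysis-plan wording plus a check of the prehospital record. The downside is small: pre-bolus values may be incomplete or, as H.2.2 allows for qualifying vitals, rest on a verbal report, so the plan should say how missing covariate values are handled.
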